9.1.15 Treatment Planning and Dosimetry

9.1.15.1 Planning System Requirements

A 3D computerised planning system capable of incorporating datasets derived from 4DCT and utilising a 3D dose calculation algorithm with pixel based inhomogeneity correction (eg convolution/superposition) will be used. Systems that can account for variation in lateral scatter in the presence of 3D-CT defined heterogeneities are required. Widely available systems that have this capability currently include Philips Pinnacle, CMS XiO, and Varian Eclipse.

Other features of the planning system must include:

- a) The planning system must be capable of handling the large CT datasets required for multiple lesions and non-coplanar beam arrangements.
- b) Dimensions of the dose calculation grid must be equal or smaller than 2.5mm.
- c) The system must be able to display summary plans.
- d) Can provide hardcopy of superimposed isodose distributions on axial CT images (sagittal and coronal planes desirable).
- e) Can provide digitally reconstructed radiographs (DRRs) with superimposed target volume, critical structure contours and treatment aperture.
- f) Provides planning data in DICOM RT or RTOG format that can be downloaded onto a CD or via a network.

For the inclusion of IMRT, the planning system must have a suitable inverse planning module with dose optimisation including non-coplanar beams. The maximum photon energy in this case will be restricted to 6MV. The planning system must have the capability to export a patient plan to a QA phantom for physical QA. All IMRT plans for patients in the study must be verified prior to treatment using physical phantom measurements.

For the use of electron radiation, the planning system must have an adequate dose calculation algorithm that can take homogeneities from CT scans into account. This will typically be a Monte Carlo based algorithm.

If Monte Carlo calculations or Boltzman radiation transport equation solvers (ACUROS™) are used the dose calculations must be dose to water to be equivalent with other dose calculations.

Please consult with the trial physicist if in doubt.

9.1.15.2 Photon Planning

Treatment plans are typically expected to be using 3D conformal radiotherapy approach. These must be delivered with at least six (6) non-opposing conformal megavoltage photon beams from linear accelerators. It is anticipated that a typical range of beam numbers would be 8 to 12, comprising of at least 6 co-planar beams and 1-2 non-coplanar beams. The treatment couch shall be included in the dosimetry of all plans. Arc therapy (including VMAT) and IMRT is allowed.

The maximum and minimum doses in the PTV shall be calculated and reported as per ICRU report 83.

A DVH must be generated for the PTV and all contoured organs at risk. DVH format and labelling of all structures must be clear.

9.1.15.3 Beam Arrangements

Radiation beams are expected to be of megavoltage quality and of 6MV, 10MV or 18MV energy. Flattening-Filter-Free modes are permitted. At least six (6) non-opposing radiation beams must be used to fulfil dosimetric criteria. Conformal arcs are allowed with a variable cumulative arc length, expected to be 200 degrees or more. The minimum field size for energy of 6mv is 3cm and for 18mv is 4cm. Smaller field sizes may be permissible when using Monte Carlo planning calculations or otherwise in consultation with trial physicist.

9.1.15.4 Shielding & Customised Blocks

Treatment must be delivered conformally using a multi-leaf collimator. Customised blocks are prohibited. The use of fields with a jaw setting of less than 3.0 cm x 3.0cm is discouraged to maintain accuracy of dose modelling, unless small field size geometry has been specifically commissioned. Shielding using multi-leaf collimation within field sizes smaller than this should be verified wherever possible, using phantom dosimetric measurements.

9.1.15.5 IMRT and Arc Therapy

The use of IMRT is generally not required for small lesions and may unnecessarily prolong treatment delivery. However, IMRT can be used (and may be required) if steep dose gradient have to be achieved. The use of arc therapies (VMAT and Dynamic Conformal Arc) are allowed to expedite treatment delivery.

9.1.15.6 Electron Planning

Electron techniques will only be used after approval from the Technical Implementation Group (TIG) of the Division of Radiation Oncology and Cancer Imaging.

Superficial lesions may be better treated using electron irradiation. In this case a single electron beam shall be used.

The electron energy and field size should be selected so that the 90% isodose line encompasses the PTV. Electrons should be prescribed and reported at the depth of maximum dose (R100). The limits for dose variation within the PTV are -10% and +10% of the dose at the reference point.

Electron energies should not exceed 12MeV. Skin dose may be a limiting factor and use of bolus will not be allowed.

The following dose values should be reported for treatment conditions:

- depth of maximum dose and nominal energy of the electron beam.
- location of and dose value at the prescription point, or ICRU Reference Point, if not located at the level of the maximum dose.

A planning CT is required to determine the tumour depth, and for mandatory outlining of the tumour bed and PTV. If planned on CT images using Monte Carlo algorithm, the maximum and minimum doses in the PTV shall be calculated and reported as per ICRU71. Junctions between electron beams and any other beam are not allowed.

The method of monitor unit calculation is at the discretion of the treating clinician, and will be determined by standard clinical practice at the Trial Site. MU calculation method will be:

- Manual calculation using data issued by the Trial Site, and including depth dose tables and factors to correct for non-standard applicator, beam shaping, and treatment distance
- Preference will be for calculation using a treatment planning system which has been commissioned for electron beams with heterogeneous tissue. MU calculations using pencil beam algorithms are generally not considered sufficiently accurate for clinical use, and an alternative (manual) method is recommended. Note that the calculated dose distribution is similarly not reliable. MU calculations using Monte Carlo algorithms may be used if that is the normal practice at the trial centre.

Therefore, if an electron field is used, the method of monitor unit calculation is at the treating clinician's discretion which is determined by the standard clinical practice at the Trial Site.

9.1.15.7 Dose Distribution/Reporting

External Beam Radiation Therapy

Dose reporting requirements follow ICRU reports 50 and 62 for photons [84, 86] . Dose and volume reporting shall follow the ICRU level 2, including the dose to ICRU reference point as well as 3D dose distributions with inhomogeneity corrections, all supported by a quality assurance program covering the entire process. The following will be reported:

- The absorbed dose at the ICRU reference point.
- The mean and maximum dose in the PTV will be calculated and reported.
- The dose to the target shall be reported as the minimum dose received by the PTV, i.e. the isodose line covering the PTV.
- A dose to 99% of the PTV (D99) and 95% of the PTV (D95) should also be reported. There will be no restriction on the upper limit of maximum dose within the PTV, however this should be ideally between 125%-143% of the prescribed dose.
- The conformity index will be reported. This is defined as the ratio between the volume encompassed by the prescription isodose and the target volume (ICRU 62).

A conformity index of 1.2 should be the ideal benchmark for radiotherapy plans when IMRT or VMAT techniques are used. A conformity index of 1.2-1.3 should be the ideal with 3D conformal treatments. A CI_{100} (volume encompassed by the 100% isodose and the target

volume) should usually be 1.6 or less if possible, and a CI₅₀ (volume encompassed by the 50% isodose and the target volume) should ideally aim to be 5 or less if possible (acknowledging that this may not be possible in all cases, and will be more difficult to achieve with smaller target volumes).

9.1.15.8 Treatment Verification and Delivery

All patients will be treated on a linear accelerator with megavoltage photon beams of a nominal energy between 6MV and 18MV.

The linear accelerator must be equipped with multi-leaf collimator of central leaf widths of 5mm or smaller projected to the isocentre. Due to the non-coplanar delivery required isocentre tolerance for quality assurance must be within a 3mm spherical volume in the planes of gantry, couch and collimator rotations.

The linear accelerator must be also equipped with verification imaging that allows visualisation of the target volume. This must be on board kV imaging, which is expected to be cone beam CT (CBCT) or superior technology. If 4D CBCT becomes available and is validated, this may be employed.

Verification imaging will be required pre-treatment, mid treatment and post treatment in all cases. Verification imaging must be capable of visualising the target with soft tissue matching for thoracic, abdominal and pelvic targets. For limb or peripheral targets, kV imaging for bony alignment is sufficient.

9.1.16 Systemic Therapy such as Chemotherapy and Systemic Targeted Agents

No systemic chemotherapy or systemic targeted agents will be allowed during the six months of treatment. Systemic chemotherapy will necessitate ceasing the study drug pembrolizumab.

9.1.17 Surgical Therapy

There are no specific surgical techniques included in this study. If a patient requires surgical fixation or procedure for spinal or long bone instability they will be ineligible for the study.

9.1.18 Dose Selection/Modification of Pembrolizumab (MK-3475)

The treatment to be used in this trial is outlined below in Table 5 below.

Table 5: Trial Treatment

Drug	Dose / Potency	Dose Frequency	Route of Administration	Regimen / Treatment Period	Use
Pembrolizumab	200 mg	Q3W	IV infusion	Day 1 of each 3 week cycle	Experimental

Pembrolizumab treatment should begin 5 days (+/- 3 days) post the last SABR treatment. 8 cycles of pembrolizumab will be delivered.

9.1.18.1 Dose Selection

The rationale for selection of doses to be used in this trial is provided in Section 7: Background and Rationale.

9.1.18.2 Dose Modification

Adverse events (both non-serious and serious) associated with pembrolizumab exposure may represent an immunologic etiology. These adverse events may occur shortly after the first dose or several months after the last dose of treatment. Pembrolizumab must be withheld for drug-related toxicities and severe or life-threatening AEs as per Table 6 below.

See Section 9.3.1 for supportive care guidelines, including use of corticosteroids.

Table 6: Dose Modification Guidelines for Drug-Related Adverse Events

Toxicity	Hold Treatment For Grade	Timing for Restarting Treatment	Treatment Discontinuation
Diarrhea / Colitis	2-3	Toxicity resolves to Grade 0-1	Toxicity does not resolve within 12 weeks of last dose or inability to reduce corticosteroid to 10 mg or less of prednisone or equivalent per day within 12 weeks
	4	Permanently discontinue	Permanently discontinue
AST, ALT, or Increased Bilirubin	2	Toxicity resolves to Grade 0-1	Toxicity does not resolve within 12 weeks of last dose
	3-4	Permanently discontinue (see exception below) ^a	Permanently discontinue
Type 1 diabetes mellitus (if new onset) or Hyperglycemia	T1DM or 3-4	Hold pembrolizumab for new onset Type 1 diabetes mellitus or Grade 3-4 hyperglycemia associated with evidence of beta cell failure	Resume pembrolizumab when patients are clinically and metabolically stable
Hypophysitis	2-4	Toxicity resolves to Grade 0-1. Therapy with pembrolizumab can be continued while endocrine replacement therapy is instituted	Toxicity does not resolve within 12 weeks of last dose or inability to reduce corticosteroid to 10 mg or less of prednisone or equivalent per day within 12 weeks
Hyperthyroidism	3	Toxicity resolves to Grade 0-1	Toxicity does not resolve within 12 weeks of last dose or inability to reduce corticosteroid to 10 mg or less of prednisone or equivalent per day within 12 weeks
	4	Permanently discontinue	Permanently discontinue
Hypothyroidism		Therapy with pembrolizumab can be continued while thyroid replacement therapy is instituted	Therapy with pembrolizumab can be continued while thyroid replacement therapy is instituted
Infusion Reaction	2 ^b	Toxicity resolves to Grade 0-1	Permanently discontinue if toxicity develops despite adequate premedication
	3-4	Permanently discontinue	Permanently discontinue
Pneumonitis	2	Toxicity resolves to Grade 0-1	Toxicity does not resolve within 12 weeks of last dose or inability to reduce corticosteroid to 10 mg or less of prednisone or equivalent per day within 12 weeks
	3-4	Permanently discontinue	Permanently discontinue
Renal Failure or Nephritis	2	Toxicity resolves to Grade 0-1	Toxicity does not resolve within 12 weeks of last dose or inability to reduce corticosteroid to 10 mg or less of prednisone or equivalent per day within 12 weeks
	3-4	Permanently discontinue	Permanently discontinue
All Other Drug-Related Toxicity ^c	3 or Severe	Toxicity resolves to Grade 0-1	Toxicity does not resolve within 12 weeks of last dose or inability to reduce corticosteroid to 10 mg or less of prednisone or equivalent per day within 12 weeks
	4	Permanently discontinue	Permanently discontinue

Toxicity	Hold Treatment For Grade	Timing for Restarting Treatment	Treatment Discontinuation
Stevens-Johnson Syndrome (SJS)	signs or symptoms	Refer to the PI and specialist	Withhold and refer the patient for specialized care for assessment and treatment.
Stevens-Johnson Syndrome (SJS)	confirmed	Permanently discontinue	Permanently discontinue
Toxic Epidermal Necrolysis (TEN)	signs or symptoms	Refer to the PI and specialist	Withhold and refer the patient for specialized care for assessment and treatment.
Toxic Epidermal Necrolysis (TEN)	confirmed	Permanently discontinue	Permanently discontinue
Immune-mediated myocarditis	signs or symptoms	Refer to the PI and specialist	Withhold and refer the patient for specialized care for assessment and treatment.
Immune-mediated myocarditis	confirmed	Permanently discontinue	Permanently discontinue

Note: Permanently discontinue for any severe or Grade 3 drug-related AE that recurs or any life-threatening event.

^a For patients with liver metastasis who begin treatment with Grade 2 AST or ALT, if AST or ALT increases by greater than or equal to 50% relative to baseline and lasts for at least 1 week then patients should be discontinued.

^b If symptoms resolve within one hour of stopping drug infusion, the infusion may be restarted at 50% of the original infusion rate (e.g., from 100 mL/hr to 50 mL/hr). Otherwise dosing will be held until symptoms resolve and the subject should be premedicated for the next scheduled dose; Refer to – Infusion Treatment Guidelines for further management details.

^c Patients with intolerable or persistent Grade 2 drug-related AE may hold study medication at physician discretion. Permanently discontinue study drug for persistent Grade 2 adverse reactions for which treatment with study drug has been held, that do not recover to Grade 0-1 within 12 weeks of the last dose.

Dosing interruptions are permitted in the case of medical / surgical events or logistical reasons not related to study therapy (e.g., elective surgery, unrelated medical events, patient vacation, and/or holidays). Participants can resume dosing for toxicity if toxicity has resolved according to Table 6 requirements, steroid dosing is 10mg or less of prednisolone, and no more than 12 weeks have passed since last dose. Patients will (or will not) receive additional pembrolizumab doses to ensure that each patient has 8 doses pembrolizumab total.

The reason for interruption should be documented in the patient's study record.

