9.5.2 Discontinuation of Study Therapy after CR

Discontinuation of treatment may be considered for participants who have attained a confirmed CR and had at least two cycles of pembrolizumab beyond the date when the initial CR was declared with the option of restarting treatment if they meet the criteria specified in Section 10.6: Second Course Phase.

After discontinuing treatment following assessment of CR, these participants should return to the site for a Safety Follow-up Visit (described in Section 10.3) and then proceed to the Follow-Up Period of the study (described in Section 10.5).

Pembrolizumab may also be discontinued or put on hold for specified AEs, see Table 7.

Additional details about follow-up after treatment completion or discontinuation are provided in Section 10.2: Visit Requirements.

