10.8.5 Serious Adverse Events

Adverse events and adverse drug reactions are considered 'serious' if they threaten life or function.

SAEs include 'Serious Adverse Drug Reactions'. During clinical investigations, adverse events may occur, which if suspected to be medicinal product related ('adverse drug reactions') might be significant enough to lead to important changes in the way the medicinal product is developed (e.g. change in dose, population, monitoring, consent). This is particularly true for reactions, which in their most severe form threaten life or function.

Due to the significant information they provide, Serious Adverse Events (including Serious Adverse Drug Reactions) require expedited reporting. SAEs are defined as any adverse event or adverse drug reaction which:

- Results in death (i.e. fatal/grade 5 CTC AE)
- Is life-threatening (i.e. grade 4 CTC AE)
- Requires inpatient hospitalisation or prolongation of existing hospitalisation*
- Results in persistent or significant disability/incapacity; or
- Is a congenital anomaly/birth defect
- Is a new cancer (that is not a condition of the study)
- Is associated with an overdose
- Other significant medical event

Note: The term 'life-threatening' in the definition of 'serious' refers to an event in which the participant was immediately at risk of death at the time of event; it does not refer to an event, which hypothetically might have caused death if it were more severe.

*An event that results in hospitalisation or prolongs an existing hospitalisation will not be considered a serious adverse event if the only reason for the hospitalisation or prolongation was:

- Administration of chemotherapy
- Administration of trial procedures
- Placement of a permanent intravenous catheter
- Hospice placement for terminal care
- Pre-trial scheduled elective surgery
- Outpatient hospitalisation for procedures such as:
 - Elective day surgery
 - Convenience purposes (e.g. transportation difficulties)

- Planned admission as part of supportive care for insertion of PEG tube or nasogastric tube for commencement of enteral feeding (i.e. did not occur following urgent admission as a result of weight loss or other patient medical events)

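### Table 6 gives opposite stop and restart instructions for life-threatening hypophysitis, and for life-threatening new-onset type 1 diabetes or grade 4 hyperglycaemia with beta cell failure

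*Combined protocol and SAP*

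**What the plan says.** All of the following is in the combined protocol and SAP.

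- **Table 6, hypophysitis row (9.1.18.2).** One line covers grades 2 to 4. Its restart cell reads "Toxicity resolves to Grade 0-1. Therapy with pembrolizumab can be continued while endocrine replacement therapy is instituted". Its discontinuation cell covers only failure to resolve, or failure to reduce steroids, within 12 weeks. Grade 4 has no line of its own.
- **Table 6, type 1 diabetes/hyperglycaemia row.** The restart column contains "Hold pembrolizumab for new onset Type 1 diabetes mellitus or Grade 3-4 hyperglycemia associated with evidence of beta cell failure". The discontinuation column contains "Resume pembrolizumab when patients are clinically and metabolically stable".
- **Note under Table 6.** "Permanently discontinue for any severe or Grade 3 drug-related AE that recurs or any life-threatening event".
- **Section 10.8.5.** One seriousness criterion is "Is life-threatening (i.e. grade 4 CTC AE". A note in the same section adds that the term "refers to an event in which the participant was immediately at risk of death at the time of event".
- **Text after Table 6.** Dosing may resume if the toxicity has resolved as Table 6 requires, steroid dose is 10 mg or less, and no more than 12 weeks have passed since the last dose. The sentence on making up missed doses states both alternatives and chooses neither.
- **Section 10.6.** Patients who had life-threatening events are excluded from second-course retreatment.

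**The concern.** The rows and the note are parts of one table and answer the same question: after this event, may the patient be dosed again? For a life-threatening event in either row, the row says yes, on conditions, and the note says never. The other sections do not settle it. Section 9.5.1 refers treatment discontinuation back to 9.1.18, and the text after Table 6 refers resumption back to the table.

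Safety is the primary objective, and these are among the most severe events the trial could see. As written, rechallenge depends on which line a site reads, and two sites could treat identical patients differently while both follow the protocol. The last dose also fixes the end of the acute adverse event window (30 days after the end of pembrolizumab, section 7.14), so the classification of later events depends on the same reading.

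**Working it through.** The plan states no figure to reproduce. The check compares the text and then counts doses.

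**Step 1: which events meet both rules**

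| Event | Row in Table 6 | Note under Table 6 | Conflict? |
|---|---|---|---|
| Hypophysitis, grade 4, immediate risk of death | Restart allowed at grade 0-1 | Permanent stop | Yes |
| New-onset type 1 diabetes, or grade 4 hyperglycaemia with beta cell failure, immediate risk of death | Resume when stable | Permanent stop | Yes |
| Grade 4 in either row without immediate risk of death | Restart or resume allowed | Depends on the meaning of life-threatening | Unclear |
| Drug-related grade 4 hyperglycaemia without beta cell failure | Falls to the all-other row: permanent stop | Permanent stop if life-threatening | No |

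A life-threatening event in the diabetes row is within what the protocol foresees: section 9.3.1 includes ketoacidosis under type 1 diabetes.

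**Step 2: is an exception implied by the layout?** Colitis, liver tests, hyperthyroidism, infusion reaction, pneumonitis, renal events and all other toxicity each have a permanent discontinuation entry covering grade 4. The hypophysitis and diabetes rows do not. Where the table does intend an exception, in the liver row, it marks it with a footnote. Neither of these rows is marked.

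**Step 3: further first-course doses for one patient**

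Inputs: 8 planned doses (9.1.18); one every 3 weeks (9.1.19); resumption no later than 12 weeks after the last dose (9.1.18.2). Let k be the last dose given before the event and r the weeks from that dose to restart.

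- Under the note: 0.
- Under the row, held doses made up: 8 - k.
- Under the row, held doses not made up: 8 - k - (r/3 - 1), with a floor of 0.

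| k | Note | Row, made up | Row, not made up, r = 3 / 6 / 9 / 12 |
|---|---|---|---|
| 1 | 0 | 7 | 7 / 6 / 5 / 4 |
| 2 | 0 | 6 | 6 / 5 / 4 / 3 |
| 3 | 0 | 5 | 5 / 4 / 3 / 2 |
| 5 | 0 | 3 | 3 / 2 / 1 / 0 |
| 7 | 0 | 1 | 1 / 0 / 0 / 0 |

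Example: k = 1 and r = 12 without make-up gives 8 - 1 - (12/3 - 1) = 7 - 3 = 4.

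The largest difference for one patient is 0 against 7. It needs an event after dose 1 and either no lost dosing slot or full make-up. For grade 3-4 hypophysitis, section 9.3.1 asks for a steroid taper of at least 4 weeks, so a lost slot is likely. The second course does not widen the gap, because section 10.6 excludes these patients.

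**The case against.** **A specific row should override a general note.** This is a reasonable reading, but the document does not state it. Hyperthyroidism is also endocrine and does have a grade 4 stop, so the table has no general endocrine exemption.

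**Life-threatening is not the same as grade 4.** This stands in part. The note uses the word and the rows use grades; the link comes from the serious adverse event section, which also requires immediate risk of death. The note could then be an overlay: life-threatening events stop, other grade 4 events follow the row. A reader might infer that every grade 4 event in these rows has two opposite instructions, or that every grade 4 hyperglycaemia does. The documents support neither, as Step 1 shows. The overlay reading is itself unstated, however, and the rows cover grade 4 without reserving life-threatening cases.

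**The secondary wording defects are smaller than they look.** This stands. The diabetes row has no discontinuation limit of its own, but the text after the table supplies the 12-week and steroid limits, so what remains is text in the wrong columns. The hypophysitis restart cell can be read in sequence: restart at grade 0-1, with continuing hormone replacement no bar. It need not contradict itself.

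**The safety result hardly moves.** This stands for the overall figure. Section 11.2.3 reports maximum grades and the proportion of patients with grade 3 or higher toxicity. A patient with a grade 4 event is already in the overall proportion, so rechallenge cannot change that patient's contribution. Counts for individual toxicities, and acute or late labels, could change.

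**Conclusion.** The contradiction holds for life-threatening hypophysitis and for life-threatening new-onset type 1 diabetes or grade 4 hyperglycaemia with beta cell failure. For such a patient the protocol permits 0 further first-course doses on one reading and at most 8 - k on the other, with a ceiling of 7. The ceiling rests on the 8-dose, 3-weekly plan; the value below it depends on length of hold and on the unresolved make-up sentence.

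Two larger claims should not be made. A reader might take the figure of less than 5% in section 11.2.9 and calculate the chance of seeing such a patient among 30. That figure concerns immune events such as hypothyroidism, pneumonitis and colitis, and the one in 11.2.10 concerns grade 3 or higher pneumonitis and colitis. Neither is a rate for the events at issue. A reader might also put a fixed number of weeks on the shift in the acute window. That shift depends on the hold and on make-up, so the documents fix no single value.

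The point is therefore about consistent treatment of individual patients after a very severe event. It does not undermine the overall grade 3 or higher estimate, but it should be corrected because safety is the trial's primary question.

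**What to change.** 1. Reconcile the Table 6 note with the hypophysitis and type 1 diabetes/hyperglycaemia rows so that a life-threatening or grade 4 event has one instruction. This can be done by naming exceptions in the note or by giving grade 4 its own line in the rows. Which rule applies is for the sponsor to decide.
2. State whether life-threatening in the note means every grade 4 event or only one with immediate risk of death.
3. Put the diabetes row's hold and resume text in the correct columns.

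Separately, section 9.5.2 refers to Table 7 for adverse event holds and discontinuations, but Table 7 covers infusion reactions only. That is a clerical correction and the point above does not depend on it.

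The cost is an amendment to one table and its note, plus the cross-reference if it is corrected at the same time. No procedure, visit or analysis is added.
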